### 6.8.3. Vital Signs

Pulse (beats/min), diastolic and systolic blood pressure (mmHg), respiration (breaths/min), and temperature (°C) will be descriptively summarized by treatment at selected visits.

Vital sign values are potentially clinically significant (PCS) if they meet both the observed value criteria and the change from baseline criteria listed in [Table 3](#) below. The number and percentage of subjects with post-baseline PCS values will be tabulated by treatment group. The percentages are to be calculated relative to the number of subjects with baseline and at least one post-baseline assessment. The numerator is the total number of subjects with at least one post-baseline PCS vital sign value. A supportive listing of subjects with post-baseline PCS values will be provided including the treatment, subject ID, study center ID, baseline, and post-baseline values. A listing of all AEs for subjects with PCS vital signs will also be provided.

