7.3.7. Abnormal Laboratory Findings

An abnormal laboratory finding in absence of any other signs or symptoms is not necessarily an AE. The investigator must review and assess all results provided by the central laboratory throughout the study in a timely manner, and determine whether any abnormal laboratory values are clinically significant (CS) or not clinically significant (NCS), and whether there are associated signs and symptoms. Laboratory abnormalities should be considered clinically significant when they occur after taking study medication, reflect a meaningful change from the screening value(s), and require active management (e.g., abnormalities that require study treatment dose modification, discontinuation, more frequent follow-up assessments, etc.).

Clinically significant laboratory abnormalities will be reported as AEs. If the abnormal laboratory finding is accompanied by signs or symptoms, report the signs and symptoms as the AE in lieu of the abnormal laboratory value. If a diagnosis is available, report the diagnosis.

7.3.8. Hypersensitivity/Anaphylactic Reactions:

Hypersensitivity and anaphylactic reactions will be monitored throughout the study, using the criteria below as defined per Sampson et al. 2006 ([Sampson, 2006](#)).

Anaphylaxis is highly likely when the following criteria is fulfilled:

1. Acute onset of an illness (minutes to several hours) with involvement of the skin, mucosal tissue, or both (e.g., generalized hives, pruritus or flushing, swollen lips-tongue-uvula).

And at least one of the following criteria:

- a. Respiratory compromise (e.g., dyspnea, wheeze-bronchospasm, stridor, reduced PEF, hypoxemia)
 - b. Reduced BP or associated symptoms of end-organ dysfunction (e.g., hypotonia [collapse], syncope, incontinence)
2. Two or more of the following that occur rapidly after exposure to a likely allergen for that patient (minutes to several hours):
 - a. Involvement of the skin-mucosal tissue (e.g., generalized hives, itch-flush, swollen lips-tongue-uvula)
 - b. Respiratory compromise (e.g., dyspnea, wheeze-bronchospasm, stridor, reduced PEF, hypoxemia)
 - c. Reduced BP or associated symptoms (e.g., hypotonia [collapse], syncope, incontinence)
 - d. Persistent gastrointestinal symptoms (e.g., crampy abdominal pain, vomiting)
 3. Reduced BP after exposure to known allergen for that patient (minutes to several hours):

- a. Systolic BP of less than 90 mm Hg or greater than 30% decrease from that person's baseline

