- f.) Full physical exam including chest auscultation
- g.) SAEs are collected from date of consent through EOS. AEs are collected from Day 0 through EOS. Number and percentage of bone fractures is captured from Day 0 through EOS. Bone fractures should be collected in the EDC as AEs, naming them using the specific guidelines in the electronic case report form completion guidelines.
- See [Section 7](#) for follow-up of AEs.
- h.) Concomitant medications and nondrug therapies must be reported beginning after informed consent is obtained and ending 60 days after the last treatment. Refer to [Section 5.2.2](#) for additional information on prohibited concomitant medications
- i.) HAHA, HAHA-NA and PK samples. See [Appendix 2](#) for PK, HAHA, and HAHA-NA sampling time points.
- j.) MFTs: Performance of Upper Limb (v. 2.0), and Hand Grip Test.
- k.) Local labs may be drawn prior to MRIs at the discretion of the investigator.
- l.) Vital signs (pulse, respiration, sitting BP, temperature) to be collected at every visit: within 30 minutes pre-infusion, and within 30 minutes after completion of infusion.
- m.) MFTs and PFTs are collected at screening and must be repeated prior to randomization and first infusion on Day 0. They may be conducted up to 3 days in advance of the Day 0 visit. The PFT results from both time points will be used to establish baseline values. The results from MFTs at Day 0 will be used to establish baseline.
- n.) Genetic Analysis samples will be collected in PAXgene tube; samples will be collected only from subjects who consent for this test. If subject consents to this optional sample, it may also be collected at an Unscheduled timepoint if it is not collected initially at Day 0.
- o.) Duchenne Video Assessment to be performed remotely within the interval between the prior scheduled study visit and next scheduled study visit.

- p.) If the subject is not going into the OLE, he should complete a final safety follow-up that consists of a visit at week 56 and a final safety follow-up phone call 60 days (+3 days) after the last infusion visit.
- q.) PFTs, MFTs, DVA and MRI only to be done at the early termination visit
- r.) Randomization may be performed within 2 days prior to Day 0 visit, after subject is confirmed eligible (see footnote “m”).

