### 5.3.2. Baseline and Change from Baseline Definitions

Baseline is defined as the last available value obtained prior to the first dose of study drug (or randomization date if no infusion received) if not specified otherwise ([Section 5.5](#)). The acceptable value on Day 1 will be used to define the baseline values. Unscheduled visits will be considered for baseline.

Change from baseline will be calculated by subtracting the baseline value from the post-dose assessment for each subject.

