**Table 3: Criteria for Potentially Clinically Significant Vital Signs**

Vital Sign Parameter	Flag	Criteria*	
		Observed Value	Change from Baseline
Systolic Blood Pressure (mmHg)	High	$\geq 170$	Increase of $\geq 20$
	Low	$\leq 90$	Decrease of $\geq 20$
Diastolic Blood Pressure (mmHg)	High	$\geq 110$	Increase of $\geq 15$
	Low	$\leq 45$	Decrease of $\geq 15$
Pulse Rate (bpm)	High	$\geq 120$	Increase of $\geq 20$
	Low	$\leq 50$	Decrease of $\geq 20$
Weight (kg)	High	-	Increase of $\geq 20\%$
	Low	-	Decrease of $\geq 20\%$

\* Except for body weight, a post-baseline value is considered as a PCS value if it meets both criteria for observed change from baseline.

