**Table 6: Analysis Visit Window for Vital Signs**

Analysis Visit	Target Day	Start Day	End Day
Baseline	Last value before the first study drug infusion (or randomization date if no infusion received)		
Day 1 post-dose	1	1	1
Week 2	15	2	22
Week 4	29	23	36
Week 6	43	37	50
Week 8	57	51	64
Week 10	71	65	78
Week 12	85	79	92
Week 14	99	93	106
Week 16	113	107	120
Week 18	127	121	134
Week 20	141	135	148
Week 22	155	149	162
Week 24	169	163	176
Week 26	183	177	190
Week 28	197	191	204
Week 30	211	205	218
Week 32	225	219	232
Week 34	239	233	246
Week 36	253	247	260
Week 38	267	261	274
Week 40	281	275	288
Week 42	295	289	302
Week 44	309	303	316
Week 46	323	317	330
Week 48	337	331	344
Week 50	351	345	358
Week 52	365	359	**

\*\* before the first study drug infusion in the OLE period or end of randomization treatment period

Note: The data on a study day with infusions will be used as a priority for summary tables whenever possible.

Note: All assessments beyond 60 days post last infusion will be excluded from summary tables or figures.

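### SAP 6.8.3 compares every post-infusion blood pressure with one value from before the first dose, so a fall across an infusion can go unflagged although a same-day pre-infusion reading exists

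*SAP*

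**What the plan says.** SAP 6.8.3 defines the potentially clinically significant (PCS) flag: "Vital sign values are potentially clinically significant (PCS) if they meet both the observed value criteria and the change from baseline criteria". The Table 3 footnote repeats the rule: "Except for body weight, a post-baseline value is considered as a PCS value if it meets both criteria for observed change from baseline". For low systolic pressure, the two conditions are a value of 90 mmHg or less and a fall of at least 20 mmHg. For low diastolic pressure, they are 45 or less and a fall of at least 15.

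The reference is set in SAP 5.3.2: "Baseline is defined as the last available value obtained prior to the first dose of study drug". Table 6 gives the same baseline for vital signs. It stays fixed for the whole main study.

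Protocol Appendix 1, footnote l, has vital signs taken at every visit "within 30 minutes pre-infusion, and within 30 minutes after completion of infusion". A subject can have up to 27 infusions.

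Three outputs in SAP 6.8.3 use the flag: the table of subjects with a post-baseline PCS value, its supporting listing, and a listing of all adverse events in PCS subjects. The only other blood pressure output there is a descriptive summary by treatment at selected visits.

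Protocol 7.3.8, item 3a, uses different numbers for reduced blood pressure within the anaphylaxis criteria: "Systolic BP of less than 90 mm Hg or greater than 30% decrease" from the person's own baseline.

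**The concern.** Readings on either side of an infusion are taken to see what happens across that infusion, and hypersensitivity, anaphylactic and infusion reactions are named safety outcomes (protocol 3.1.1.3, SAP 4.3). The Table 3 rule does not use the pair. It asks whether the post-infusion value is low and has fallen far enough from a reading that may be a year old. A subject whose first pre-dose reading happened to be low, or whose usual pressure has since risen, needs a larger same-day fall to be flagged.

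Other planned outputs do not fill the gap. A summary of values by visit does not show isolated drops, and Table 6 has a separate post-dose row for Day 1 only. SAP 6.8.6 identifies special safety events from a preferred-term list, so blood pressure readings do not enter. The listing of adverse events for PCS subjects relies on the same flag, so a missed reading also drops out of that cross-check. At stake is how completely infusion-related falls in blood pressure are described by arm.

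**Working it through.** **Inputs.** SAP Table 3: low systolic pressure is v ≤ 90 with a fall ≥ 20; low diastolic is v ≤ 45 with a fall ≥ 15. SAP 5.3.2 and Table 6: the fall is b − v, where b is the last value before the first dose. Protocol Appendix 1: a same-day pre-infusion value p also exists. The plan states no figure to reproduce.

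**Where the references disagree (systolic).**
- Present rule: flag if v ≤ 90 and b − v ≥ 20, that is v ≤ min(90, b − 20).
- Same-day reference: flag if v ≤ 90 and p − v ≥ 20, that is v ≤ min(90, p − 20).
- A same-day fall that meets Table 3's own numbers is missed when v ≤ 90 and b < v + 20 ≤ p. Since v + 20 is at most 110, this needs a baseline below 110 and a higher pre-infusion value.

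| b | p | v | p − v | b − v | Present rule | Same-day |
|---|---|---|---|---|---|---|
| 100 | 115 | 88 | 27 | 12 | not flagged | flagged |
| 115 | 100 | 88 | 12 | 27 | flagged | not flagged |
| 100 | 100 | 82 | 18 | 18 | not flagged | not flagged |

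Row 2 shows why the present rule should stay: each reference catches cases that the other misses. Row 3 shows what a same-day row would not change. The same logic holds for diastolic pressure: b = 55, p = 62, v = 44 is a same-day fall of 18 but only 11 from baseline.

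**How often, under assumptions.** The documents give no blood pressure variability. Assume a true infusion fall of 25 mmHg.
- Fixed reference: two readings on different days, each with within-subject SD s, have a difference with SD √2·s. P(fall ≥ 20) = Φ((25 − 20)/(√2·s)). For s = 5: Φ(5/7.07) = Φ(0.71) = 76%. For s = 9: Φ(5/12.73) = Φ(0.39) = 65%.
- Same-day reference: the day's common deviation cancels, leaving a residual SD e per reading. P = Φ(5/(√2·e)). For e = 2: Φ(1.77) = 96%. For e = 3: Φ(1.18) = 88%. For e = 4: Φ(0.88) = 81%.
- If the paired readings are as unrelated as readings on different days (e = s), the two formulas coincide and nothing is gained.

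A simulation restricted to post-infusion readings below 90 agrees in direction (mean 110, between-subject SD 10, within-subject SD 5 to 9, fall of 25). With paired readings close apart from the fall, the same-day reference caught about 97%, against 77% to 82% for the fixed one. The percentages are higher because selecting readings below 90 favours larger observed falls.

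**Background flags.** A subject with all 27 infusions has 27 × 2 − 1 = 53 post-baseline readings. With no drug effect, the same assumed mean and SDs, and readings independent of one another, roughly 2% to 29% of subjects had at least one low systolic flag under the present rule and 1% to 29% under the same-day rule. A pair that moves together would lower the second figure.

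**Table 3 beside protocol 7.3.8.** At baseline 100, readings of 81 to 89 meet the below-90 part of item 3a but not Table 3. At baseline 108 only 89 does, and from 109 upward none does. The over-30% part differs at the other end: at baseline 140, a fall to 94 is 46/140 = 32.9% but stays above 90. The SAP does not comment on the difference.

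**The case against.** The strongest reply is that a rule requiring both a level and a change is a reasonable screening choice, because it keeps ordinary variation out of the table. The protocol asks only for clinically significant changes from baseline in vital signs to be summarized. Investigators monitor hypersensitivity with the protocol 7.3.8 criteria, and subjects are asked about adverse events before and after each infusion (protocol 5.1.3). SAP 6.8.1 and 6.8.6 tabulate adverse events and special safety events by arm, and SAP 5.1 lists all collected data. A symptomatic fall should therefore reach the report without a PCS flag. Most of this stands, and it limits the stakes. It does not cover a fall that nobody reports as an event: questioning is general (protocol 7.3.2), and a data listing is not a comparison by arm.

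A reader might infer that the SAP contradicts the protocol's own definition of hypotension. It does not. Item 3a applies after exposure to a known allergen and serves to recognize anaphylaxis, whereas Table 3 screens vital signs. The difference is unreconciled, but it is not a contradiction.

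A reader might also want the two conditions joined by \"or\" with the item 3a numbers. That would choose a clinical threshold, which is not for this review. It also has a cost: under the no-effect assumptions above, such a rule flagged about 20% to 52% of subjects, enough background in both arms to obscure a difference.

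**Conclusion.** The point holds as a reporting gap. Post-infusion blood pressures are judged against a fixed pre-first-dose value, no planned table uses the same-day pair, and a fall that meets Table 3's own numbers across an infusion can go unflagged. That much follows from the text and arithmetic alone.

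The size is uncertain. The gain from a same-day reference (65% to 76% rising to 81% to 96% for a true 25 mmHg fall) rests on assumed SDs, and on readings around one infusion agreeing better with each other than with a reading from months earlier. If they do not, the gain is nil.

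It is also tempting to take the share of subjects with baseline systolic pressure below 108 as a miss rate, since a reading of 88 goes unflagged in them. Under assumed means of 105 to 120 and SDs of 10 to 12, that share runs from 62% down to 12%. It describes an assumed baseline distribution and one chosen reading; it is not the proportion of events missed. Nor do the documents support saying that smaller or younger subjects are more affected: they give no blood pressure by age or size, and adults are eligible.

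No efficacy endpoint or hypothesis test is touched. This is a cheap, worthwhile improvement to a descriptive safety table.

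**What to change.** In SAP 6.8.3, keep the present PCS row and add one row by arm: subjects with at least one post-infusion blood pressure that meets the existing Table 3 criteria, with the change measured from the same-day pre-infusion value. Carry the same flag into the supporting listing and the listing of adverse events for flagged subjects. State how a missing pre-infusion reading is handled.

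The sponsor should also reconcile Table 3 with protocol 7.3.8, item 3a, or state in one sentence why the two differ. Which threshold is appropriate is for the sponsor to decide.

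The cost is SAP wording and one extra descriptive row from data already collected, plus some extra background flags in both arms. The row should be read as a comparison between arms, not as a count of clinical events.

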**Table 3: Criteria for Potentially Clinically Significant Vital Signs**

Vital Sign Parameter	Flag	Criteria*	
		Observed Value	Change from Baseline
Systolic Blood Pressure (mmHg)	High	$\geq 170$	Increase of $\geq 20$
	Low	$\leq 90$	Decrease of $\geq 20$
Diastolic Blood Pressure (mmHg)	High	$\geq 110$	Increase of $\geq 15$
	Low	$\leq 45$	Decrease of $\geq 15$
Pulse Rate (bpm)	High	$\geq 120$	Increase of $\geq 20$
	Low	$\leq 50$	Decrease of $\geq 20$
Weight (kg)	High	-	Increase of $\geq 20\%$
	Low	-	Decrease of $\geq 20\%$

\* Except for body weight, a post-baseline value is considered as a PCS value if it meets both criteria for observed change from baseline.

#### 6.8.4. Physical Examination

Clinically significant changes in PE results from baseline will be summarized by treatment over visit. A shift table will be provided if data appropriate. A listing of clinically significant changes in PE results from baseline will be provided.

#### 6.8.5. Electrocardiogram

ECG results will be provided in a listing only.

#### 6.8.6. Special Safety Events

Treatment-emergent special safety events including:

1. Hypersensitivity (any time)
2. Infusion reactions (24 hours: on day of infusion or 1 day post any study drug infusion)
3. Anaphylactic reactions (24 hours: on day of infusion or 1 day post any study drug infusion)

Items 1 and 2 include both hypersensitivity and angioedema events. Both items will be listed and summarized similarly to TEAEs:

- Events by event type, SOC, PT, and maximum severity,
- Events by event type, SOC, PT, and subgroups (same as TEAEs).

Items 3 will be listed and summarized by treatment and PT only.

The preferred term list for these special safety events will be finalized prior to database lock.

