The Investigator or a designee with proper medical training must be either present, or immediately available, during the first IP infusion and observation period (approximately 1 hour after the end of IP infusion) for each subject. If a subject has a significant infusion reaction, the infusion rate may be slowed or temporarily stopped, depending on the severity of symptoms. If a subject experiences a significant infusion reaction and continues Study Drug dosing, a physician should be immediately available during all subsequent infusions and observation periods at the site. Subjects who experience an infusion reaction will not be allowed to participate in Home Health Care (HHC). If the Investigator wishes to use premedication, (e.g., antihistamines, nonsteroidal anti-inflammatory drugs (NSAIDs)) for a subsequent infusion should be discussed with the sponsor Medical Monitor or designee. Infusions are to be continued until the total volume of the IP infusion has been administered. Subjects will remain at the study site for 1 hour after the end of the IP infusion for clinical observation for all study infusions.

Study Drug will be administered at a hospital or ambulatory setting with adequate facilities for managing medical emergencies. Medications for the treatment of acute reactions, including anaphylaxis, must be available to study site staff for immediate use. Medications for the treatment of acute reactions, including anaphylaxis, will be maintained at the subject's home for access by HHC nurse. There is no specific treatment for a pamrevlumab overdose or infusion reaction. Signs and symptoms should be managed with appropriate standard of care treatment.

The Sponsor may consider the use of properly trained home health care staff to administer the infusions of study drugs at the subject's home and corresponding study assessments during the

conduct of the study (after the completion of three infusions without safety concerns), consistent with institutional regulations and policies (see Section 5.1.4 for details).

The following procedures must be performed prior to each infusion:

- Vital signs (sitting blood pressure [BP], pulse, respiration, and temperature) within 30 minutes before starting the infusion
- Query subject and assess TEAEs
- Record concomitant medications

The following procedures must be performed after each infusion:

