#### **5.5. Analysis Visit Windows**

In accordance with FDA/EMA Guidance: During the COVID-19 pandemic, the visit modality (e.g.: in-person versus remotely) and scheduling may be adjusted and conducted at the discretion of the Investigator, in accordance with the site's rules and recommendations, and using all necessary precautions. If a visit must be done remotely, it can be conducted with any technology available to the site and study subjects, such as via tele-health visits, phone calls, etc.

Analysis visits, instead of the nominal visits from case report form (CRF), derived from visit dates and visit time windows will be used in the by-visit analyses. Unscheduled visits within a visit window (defined in [Appendix 2](#)) will be grouped into the closest scheduled visits based on the visit date. For subjects who have more than one measurement at a certain analysis visit, the measurement closest to the target date or the later assessment if there is a tie will be used, with the following exceptions:

- Liver function tests, such as Alanine Aminotransferase (ALT), Aspartate Aminotransferase (AST), Gamma-Glutamyl transferase (GGT), Alkaline Phosphatase (ALP), and total bilirubin, in which the maximum value will be used.
- Vital signs: the values on the infusion days will be used if applicable.
- Spirometry data: the Best Test Read (BTR) values will be used for analysis.

Efficacy parameters will be summarized by analysis visit defined by the following assessment windows ([Appendix 2](#)). The date of the first dose will be considered as the date of Day 1 for all analyses. Subjects will receive study drug every 2 weeks. The visit window for these visits is  $\pm 3$  days. Duchenne Video Assessment is to be performed in the subject's home up to 14 days prior to the scheduled study visit.

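### Anaphylactic reactions are counted from a preferred-term list, and the protocol's own combination criteria are not applied to that count

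*SAP*

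**What the plan says.** Hypersensitivity and anaphylactic reactions are a named safety assessment in both documents (protocol 3.1.1.3, SAP 4.3).

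**Protocol 7.3.8.** "Hypersensitivity and anaphylactic reactions will be monitored throughout the study, using the criteria below". Three criteria follow:
1. Acute skin or mucosal involvement, plus respiratory compromise or reduced blood pressure.
2. Two or more of skin or mucosal, respiratory, blood-pressure and gastrointestinal signs soon after exposure to a likely allergen.
3. Reduced blood pressure after exposure to a known allergen, given as "Systolic BP of less than 90 mm Hg or greater than 30% decrease" from the person's baseline.

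The time frame is minutes to several hours.

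**SAP 6.8.6.** The third special safety event is defined by its window: "Anaphylactic reactions (24 hours: on day of infusion or 1 day post any study drug infusion". Cases come from a term list: "The preferred term list for these special safety events will be finalized prior to database lock". Neither the list nor a rule for choosing its terms is in the SAP. Anaphylaxis is tabulated by treatment and preferred term only. The section does not cite protocol 7.3.8 or plan a review of cases against it, and SAP 7 does not record a change.

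**Vital signs.** Protocol Appendix 1 has them taken "within 30 minutes pre-infusion, and within 30 minutes after completion of infusion". SAP 6.8.3 and Table 3 flag a low systolic value as potentially clinically significant (PCS) only if it is at most 90 mmHg and at least 20 mmHg below baseline.

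**The concern.** The protocol's first two criteria are rules about combinations of signs. A list of preferred terms works one coded event at a time, and the SAP adds no rule that joins events within a subject and an infusion. The reported number of anaphylactic reactions may therefore differ from the number of subjects who met the definition the protocol set for this topic. Both arms are counted the same way, so this is not bias by design. But anaphylaxis to an infused antibody is an outcome where a handful of cases shapes the safety conclusion, and the count should rest on the stated definition.

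**Working it through.** The documents state no expected anaphylaxis rate and no sensitivity for the term list, so there is no figure to reproduce. The check sets the texts side by side, then does arithmetic on the two blood-pressure rules.

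**Step 1: can a case meet the protocol and miss the list?** Take a subject with generalized hives and wheeze during an infusion, entered as two adverse events, urticaria and wheezing. Criterion 1 is met: skin involvement plus respiratory compromise. Neither entry is an anaphylaxis term, so unless the list contains such symptoms the subject is not in the anaphylaxis count. Protocol 7.3.2 asks for a unifying diagnosis where possible but does not require one, and it rules out directed questioning about any specific event.

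**Step 2: can a case miss the protocol and be on the list?** If the list does contain symptom terms such as urticaria, isolated urticaria on the day after an infusion would count, although one sign satisfies neither combination criterion. The window is also wider than the protocol's: the infusion day plus the next calendar day spans up to 2 x 24 = 48 hours, against minutes to several hours.

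**Step 3: does the PCS table catch the blood-pressure cases?** Let b be baseline and v the post-infusion systolic reading, in whole mmHg.
- Protocol threshold: v < 90, or (b - v)/b > 0.30.
- PCS low: v <= 90 and b - v >= 20.

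| Baseline b | Highest v meeting protocol threshold | Highest v flagged PCS low | Meets protocol, not PCS |
|---|---|---|---|
| 95 | 89 | 75 | 76 to 89 |
| 100 | 89 | 80 | 81 to 89 |
| 105 | 89 | 85 | 86 to 89 |
| 110 to 125 | 89 | 90 | none |
| 130 | 90 | 90 | none |
| 135 | 94 | 90 | 91 to 94 |
| 140 | 97 | 90 | 91 to 97 |
| 145 | 101 | 90 | 91 to 101 |

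(Baselines were checked in steps of 5.) Two worked rows:
- b = 100, v = 85: 85 < 90, so the protocol threshold is met. The fall is 100 - 85 = 15, below 20, so it is not PCS.
- b = 140, v = 97: the fall is 43, and 43/140 = 30.7%, so the threshold is met. 97 is above 90, so it is not PCS.

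For baselines of 110 to 130 the rules almost coincide; from 110 to 125 a reading of exactly 90 is PCS only. They part at lower and higher baselines because PCS requires both conditions while the protocol threshold requires either. Meeting the threshold alone is not anaphylaxis, since criterion 3 also needs a reduction after exposure to a known allergen. The table shows only that the PCS output cannot stand in for that part of the definition.

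**The case against.** The strongest reply is that the protocol criteria already act upstream. Investigators are given them for monitoring, and diagnoses are to be recorded where signs share a cause, so a reaction meeting 7.3.8 should reach the database as anaphylaxis. If it is entered as symptoms, it still appears in the adverse-event tables and may fall under hypersensitivity, which has no time limit. Adverse events leading to interruption or discontinuation have their own tables (SAP 6.8.1), interruptions and their reasons are summarised (SAP 6.5.1), and a data monitoring committee reviews safety. Fixing the list before database lock guards against choosing terms after seeing results.

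Most of this stands: such events would not be invisible, and investigators' diagnoses will reduce the gap. What it does not do is put a symptom-coded case into the anaphylaxis count, or remove an isolated symptom from it.

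Three stronger readings are tempting, and the documents do not support them.

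- *A reader might infer that only post-infusion vital signs are kept.* SAP 5.5 says "the measurement closest to the target date or the later assessment if there is a tie will be used", but it then lists vital signs as an exception that uses infusion-day values without choosing before or after. The rule governs by-visit analyses, whereas the PCS count in 6.8.3 takes any post-baseline value.
- *A reader might infer that infusion reactions are confined to hypersensitivity and angioedema terms.* The text is "Items 1 and 2 include both hypersensitivity and angioedema events". To include is not to limit, and the list is not shown, so nothing can be said about fever, chills or hypotension.
- *A reader might infer that the SAP also displaced protocol criteria for infusion reactions.* The protocol has none. Section 5.1.3 covers management only: "If a subject has a significant infusion reaction, the infusion rate may be slowed or temporarily stopped".

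**Conclusion.** The concern holds for anaphylaxis, and as a low-cost improvement. The plan's count rests on a term list in a two-calendar-day window, the protocol's definition rests on combinations of signs, and no planned step reconciles them. Misclassification is possible in both directions.

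Its size cannot be given. A reader might express the stake as one missed case among about 48 treated subjects, 0/48 against 1/48. That assumes the miss and fixes its direction, and no event rate or list content in the documents supports either.

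The conclusion rests on two assumptions: that some reactions may be entered as separate signs, which protocol 7.3.2 allows, and that no combination rule accompanies the unseen list, since the SAP mentions none. If the list turns out to be paired with a review against 7.3.8, the point reduces to saying so in the SAP.

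**What to change.** Add to SAP 6.8.6, before unblinding:

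1. From the adverse-event and vital-sign data already collected, identify every subject who, in the post-infusion window, has events in two or more of the protocol 7.3.8 categories (skin or mucosal, respiratory, blood pressure, gastrointestinal) or a reading that meets its blood-pressure criterion.
2. Within the existing medical review, and blinded to treatment, classify each candidate against protocol 7.3.8. Give the reviewer the same-day pre-infusion reading, so that a pressure that was already low is not taken for a fall.
3. Report the criteria-based count by arm beside the term-list count.

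As a minor addition, tabulate the same-day change in vital signs from before to after infusion. Both readings are already taken at each infusion.

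The cost is SAP wording, a few hours of blinded review and one or two extra tables. No new data are needed, and the planned term-list summary stays as it is.
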